### 3. Methods

#### 3.1 Study design

This will be a prospective multi-centre open-label clinical trial at 10 pediatric centres that are members of the SIC network and the C council which is comprised of the heads of the 16 pediatric oncology and blood and marrow transplantation programs in Canada. Each participating site is run by a Site Investigator in conjunction with a nurse coordinator (SIC nurse). The coordinating site will be the Canadian Center for Vaccinology at the IWK Health Centre, Halifax, NS.

Children who were diagnosed with ALL at  $\geq 1$  year of age, are within 3-12 months of completing chemotherapy, and have not received immunizations other than influenza since completing chemotherapy will be eligible. As most centres initiate immunization at 6 months post-chemotherapy, children will be enrolled and immunized at the 6-month visit, where possible. Children can be enrolled as late as 12 months post-chemotherapy if they meet all other eligibility criteria. All participants will undergo a clinical assessment, and immunologic and serologic testing for pneumococcus, tetanus, pertussis and varicella. They will then be immunized with PCV13, DTaP-IPV-Hib, regardless of immunization history [unless PPV23 was received within the prior 12 months (see section 3.2.1)]. Other routine vaccines required as per provincial and centre-specific immunization policies will also be administered. Pneumococcal polysaccharide vaccine (PPV23) will be administered approximately 2 months after PCV13. Repeat serologic testing will be conducted at 2-3 months and 12-15 months after DTaP-IPV-Hib and PCV13 immunization to assess short and long-term immune responses.

Study visits and bloodwork will be coordinated with routine blood draws wherever possible. Baseline antibody titres will be compared to age-matched immunocompetent controls. Vaccine responses will be compared to healthy vaccine recipients in published clinical trials. Multivariable analysis will be conducted to identify predictors of low baseline antibody titres after chemotherapy and poor immune responses to vaccination.

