**Table 3. Schedule of Study Activities**

Procedures for patients	Visit 1	Follow up Phone call 8-10 days post V1	Follow up Phone call 30-33 days post	Visit 2 2 months Post V1†	Follow up Phone call 8-10 days post V2	Follow up Phone call 30-33 days post V2	Visit 3 12-15 months post V1
-------------------------	---------	--	--------------------------------------	---------------------------	--	---	------------------------------

			V1				
Informed Consent	X*						
Past Medical History	X*						
Current Health Status	X*						
Medications	X*						
Review of Immunization Records	X*						
Vital signs	X						
Immune Markers (CBC, qIgs, T and B subsets)	X						
Vaccine serologies	X			X			X
PCV13 and DTaP Immunization	X						
PPV23 immunization				X			
Phone Call (adverse events)		X	X		X	X	

qIgs: quantitative immunoglobulins; \*Maybe be conducted as part of a screening visit at 3-5 months post-treatment. †Visit can occur up to 3 months post-immunization.

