#### Visit 1 (Baseline assessment):

After providing informed consent, participants with ALL will undergo a standardized health evaluation, including review of past medical history, current health status, and medications, and vital signs as part of routine clinical care. Immunization records will be obtained from the participant's vaccination card, medical chart, family physician or public health. Varicella serology results at time of ALL diagnosis (measured as part of routine care) will be obtained from the medical record. The above activities can be completed as part of a separate screening visit at 3-5 months post-treatment, with visit 1 then scheduled at 6 months post-treatment to collect bloodwork and administer immunizations.

Baseline laboratory evaluation will include complete blood count, quantitative serum immunoglobulins (IgA, IgG, IgM), peripheral blood T and B cell subsets and antibody titres to the following vaccine antigens: tetanus toxoid, pertussis toxin (PT), varicella, and pneumococcal serotype-specific IgG. If serum immunoglobulins, T and B cell subsets or antibody titres were measured within one month prior to enrollment, those results can be obtained as baseline results, in lieu of repeating the testing.

Participants will be immunized with PCV13, DTaP-IPV-Hib (If DTaP-IPV-Hib is not available, DTaP-IPV and Hib may be administered separately) in addition to the "catch-up" vaccines

required according to the schedule currently followed at their centre. Vaccines will be administered in the SIC or oncology clinic, where possible, but may be administered by the primary care physician or public health. Vaccines must be administered within two months of the baseline assessment and within 12 months of completing chemotherapy. The SIC nurse will obtain vaccination details from the vaccine provider within 7 days of the vaccination visit.

Telephone follow-up for AEFI:

A study nurse will contact caregivers (or participants where appropriate) by telephone on days 8-10 and 30-33 after each immunization to elicit local and systemic symptoms and their severity using a standard questionnaire.

Visit 2 (2 months post-immunization)

Serologic responses will be measured to tetanus, PT and pneumococcus. PPV23 will be administered. If necessary, this visit can be delayed to 3 months post-immunization.

Visit 3 (12-15 months after visit 1):

Serologic responses will be measured to tetanus, PT and pneumococcus.

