### **6.3 Variables**

#### **6.3.1 Outcomes**

The primary outcomes are the proportion of participants with protective titres ( $\geq 0.35 \mu\text{g/ml}$ ) to the PCV13 serotypes tested, at baseline (compared to age-matched controls), 2 months and 12-15 months post PCV13+PPV23.

Secondary outcomes include baseline GMTs and frequency of protective titres to varicella, pertussis toxin and tetanus among ALL patients versus controls, short-term (baseline to 2 months after vaccination) and long-term (baseline to 12-15 months) vaccine responses to DTaP, based on GMT ratios, the proportion of subjects with protective titres (e.g., tetanus, varicella) and/or the

proportion with an adequate immune response (defined as GMT ratio  $\geq 4$  at 2 and 12-15 months post-vaccination).

**Safety assessment:** The primary outcome is frequency of AEFI of moderate impact or greater (see definitions in section 5.3). The secondary outcomes are frequency of any AEFI and frequency of AEFI deemed to be causally associated with vaccination.

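### Visit 3 is counted from Visit 1 rather than from vaccination, so the 12-15 month primary outcome can fall up to 2 months early after PCV13 and does not match its PCV13+PPV23 label

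*Combined protocol and SAP*

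**What the plan says.** Section 4.2 heads the first visit "Visit 1 (Baseline assessment" and expects vaccination in a study clinic where possible. It also says that vaccines "may be administered by the primary care physician or public health", and sets the limit: "Vaccines must be administered within two months of the baseline assessment and within 12 months of completing chemotherapy".

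The late blood draw has three different starting points:

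- **Visit 1.** Table 3 has "Visit 3 12-15 months post V1" and the section 4.2 text has "Visit 3 (12-15 months after visit 1".
- **PCV13 and DTaP-IPV-Hib.** Section 3.1: "Repeat serologic testing will be conducted at 2-3 months and 12-15 months after DTaP-IPV-Hib and PCV13 immunization".
- **PCV13+PPV23.** The primary outcome in section 6.3.1 reads "2 months and 12-15 months post PCV13+PPV23", and section 5.2 uses the same label for the late sample.

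PPV23 is given at Visit 2, about 2 months after PCV13 (section 3.1), and that visit may slip to 3 months after immunization (section 4.2).

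For Visit 2 and the first two safety calls, the Table 3 column heads count from Visit 1. The text counts from immunization: section 4.2 has "Visit 2 (2 months post-immunization", and sections 3.1, 4.2 and 5.3.2 all time the calls that way.

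**The concern.** The late pneumococcal sample is part of the primary outcome, and the same visit supplies the long-term tetanus and pertussis results. The visit rule that staff would follow does not guarantee the interval in the outcome definition. A sample taken early, reported as 12-15 months, would make persistence look better than it is if titres are still falling. The comparison with published trials in healthy children (section 6.4) also depends on like sampling times.

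The planned analysis would not reveal the mismatch. Sections 6.3.2 and 6.4 use the interval from last chemotherapy to immunization, and section 6.4 stratifies baseline results by interval since last vaccination. Neither lists the time from study vaccination to the follow-up draws.

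The table-versus-text conflict matters for a different reason. The calls feed the primary safety outcome, and a call counted from Visit 1 can come before a delayed vaccination.

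**Working it through.** **Inputs, in months**

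- d, delay from Visit 1 to PCV13/DTaP-IPV-Hib: 0 to 2 (section 4.2).
- V3, Visit 3 after Visit 1: 12 to 15 (Table 3; section 4.2).
- g, PCV13 to PPV23 at Visit 2: 2 to 3 (sections 3.1 and 4.2).

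**Formulas**

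- Time since PCV13 = V3 − d.
- Time since PPV23 = V3 − (d + g).

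**The plan's own figure.** With d = 0, time since PCV13 is 12 − 0 = 12 to 15 − 0 = 15. The stated 12-15 months is reproduced, but only from PCV13 and only with no delay.

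**Results under the Visit 3 rule as written**

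| Delay | Since PCV13/DTaP-IPV-Hib | Since PPV23 |
|---|---|---|
| none | 12 to 15 | 12 − 3 = 9 to 15 − 2 = 13 |
| full 2 months | 12 − 2 = 10 to 15 − 2 = 13 | 12 − (2 + 3) = 7 to 15 − (2 + 2) = 11 |
| any allowed (0 to 2) | 10 to 15 | 7 to 13 |

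**Where the shortfall comes from.** Against the 12-month lower limit, the worst case is 12 − 10 = 2 months from PCV13, all of it due to delay. From PPV23 it is 12 − 7 = 5 months. Up to 3 of those come from PPV23 being given at Visit 2 and exist with no delay; the delay adds at most 2.

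**Table 3 column heads taken literally.** With a 2-month delay, Visit 2 at 2 months after Visit 1 falls 2 − 2 = 0 months after PCV13. The call on days 8-10 precedes vaccination for any delay over 10 days, and the call on days 30-33 for any delay over 33 days. These results cannot be combined with the 7-month figure, which assumes that Visit 2 follows the text and is counted from immunization.

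**Counting from the actual PCV13 date (section 3.1).** Visit 3 falls 12-15 months after PCV13, 12 − 3 = 9 to 15 − 2 = 13 months after PPV23, and 12 + 0 = 12 to 15 + 2 = 17 months after Visit 1. Changing the anchor therefore removes the PCV13 shortfall but not the mismatch with a label read from PPV23.

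**The case against.** The best defence is that Table 3 is a summary. It marks PCV13 and DTaP under Visit 1, so in the standard case Visit 1 and immunization are the same day and the two ways of counting agree. That stands for children vaccinated at Visit 1. It does not cover the delay that section 4.2 expressly allows, and for Visit 3 the section 4.2 text repeats the Visit 1 anchor instead of correcting it.

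A second defence is that PCV13+PPV23 names the regimen received, not the start of the clock. This is plausible: the 2-month sample is drawn at the visit where PPV23 is given, so it cannot be 2 months after PPV23. But sections 5.2 and 6.3.1 do not say so, and a reader of the results would not know that the sample is 9-13 months after PPV23 even when nothing is late.

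Third, the shift from PCV13 is at most 2 months against a window 3 months wide, and the documents give no rate of antibody decline. That is right, and it limits the point.

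Two stronger readings are tempting. A reader might infer that all visits and calls run from Visit 1, so that short-term responses will be measured too early. The documents do not support this: sections 3.1, 4.2 and 5.3.2 time Visit 2 or the calls from immunization, and the Table 3 footnote does so for the upper limit of Visit 2. The 7-day rule for obtaining vaccination details also leaves time for a call on days 8-10 after vaccination. A reader might also infer that delayed vaccination alone puts the primary outcome well short of 12 months. It accounts for at most 2 months; the rest of the PPV23 gap is built into giving PPV23 at Visit 2.

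**Conclusion.** The inconsistency is real and touches a primary outcome, but its size is modest. Under the Visit 3 rule as written, the late sample falls 10-15 months after PCV13/DTaP-IPV-Hib instead of 12-15, with a shortfall of at most 2 months confined to children with delayed vaccination. It falls 9-13 months after PPV23 with no delay and 7-13 months over all allowed delays, so the label is not met from PPV23 over the full window in any case. The Table 3 column heads for Visit 2 and the first-round calls are a table-versus-text conflict that matters only when vaccination is delayed.

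This rests on three assumptions:

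- The baseline assessment is Visit 1, as its heading says.
- A full 2-month delay is available only if Visit 1 falls no later than 12 − 2 = 10 months after chemotherapy, because of the 12-month limit.
- The PPV23 intervals apply only to children given PPV23 at Visit 2; section 4.6.2 does not reimmunize those who have already had it.

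The documents do not say how many children will be vaccinated late or off site. The direction of any bias in persistence depends on waning between the actual and nominal times. No sample-size or power figure depends on visit timing.

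**What to change.** 1. Reconcile Table 3 and the Visit 3 text in section 4.2 with section 3.1, so that both follow-up blood draws and the safety calls are counted from the recorded immunization date.
2. State in sections 5.2 and 6.3.1 which dose starts the 12-15 month clock, and report the actual interval since PPV23 alongside the result.
3. In section 6.4, analyse the follow-up samples using actual days since vaccination, and examine samples outside the window in a sensitivity analysis.

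The data are already collected: the study nurse obtains vaccination details within 7 days of vaccination (section 4.2), and specimens carry the draw date (section 4.3). No extra visit or sample is needed. The costs are that Visit 3 may fall up to 17 months after Visit 1 for children with delayed vaccination, which affects the follow-up timeline and coordination with routine oncology visits, and a little more analysis work.

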## **2. Objectives**

- To identify risk factors for low baseline antibody titres to pneumococcal serotypes, tetanus, pertussis toxin, and varicella in previously immunized children diagnosed with ALL at  $\geq 1$  year of age who completed chemotherapy within 6-12 months, as compared to immunocompetent age-matched controls.
- To assess short and long-term immune responses to PCV13 followed by PPV23 in children immunized 6-12 months after completing chemotherapy for ALL.

- To assess short and long-term immune responses to a DTaP-IPV-Hib booster in children immunized 6-12 months after completing chemotherapy for ALL.
- To estimate the frequency of medically-attended AEFI in children immunized after completing treatment for ALL.

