## 3.2 Subjects, recruitment and consent

### 3.2.1 Cases

#### *Inclusion criteria*

- Diagnosed with standard risk, high risk or very high risk ALL
- Age at diagnosis:  $\geq 1$  year of age (age at enrollment:  $\geq 3$  years)
- Completed chemotherapy 3 to 12 months prior to enrollment
- No evidence of ALL relapse or secondary malignancy
- No known primary immunodeficiency
- No receipt of pneumococcal or tetanus-containing vaccines since completing chemotherapy
- No history of allergy to any component of PCV13
- Caregiver and/or participant is English or French-speaking and able to provide written informed consent

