### 3.2.2 Controls:

#### *Inclusion criteria*

- Children 3-18 years of age, age-matched to cases
- Caregiver and/or participant is English or French-speaking and able to provide written informed consent

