### 3.2.3 Recruitment and Consent

The oncologists and/or clinic nurses will identify potentially eligible subjects with ALL.

Caregivers of eligible patients will then be approached to participate in the study during routine outpatient visits to the pediatric oncology clinic. The consent form will be reviewed with caregivers by a research nurse, oncologist or oncology clinic nurse. Participants' and caregivers' questions will be answered and written informed consent will be obtained.

Children 3-18 years of age who are not immunocompromised will be recruited as controls from among children requiring venous blood draws in the outpatient laboratory, siblings of participants with ALL, prior study participants who have consented to future contact, and other methods depending on the study site. Caregivers of potentially eligible children will be approached by study staff in the outpatient laboratory or clinic, or contacted by the study team via telephone, email or mail and invited to participate. As above, written informed consent will be obtained after the consent form is reviewed and the participants' and caregivers' questions have been answered. Controls will be frequency age-matched to cases to ensure that the age distribution of cases and controls is similar. Three participating sites will be responsible for recruiting approximately 75 control subjects. The coordinating site will conduct the age-matching of controls to cases.

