Blood sampling will be coordinated with routine blood draws, which are conducted at most follow up visits.

Controls:

Past medical history will be reviewed for any excluding conditions and once informed consent has been obtained, immunization records will be obtained as described above. Serum will be collected to measure “baseline” antibody titres to tetanus, PT, varicella, and pneumococcal serotypes, based on the vaccinations received. There will be no further follow-up of controls.

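### Baseline titres: cases are tested for every antigen, controls apparently only for those in their own vaccines, and section 6.4 sets no common antigen- or serotype-specific denominator

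*Combined protocol and SAP*

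**What the plan says.** All references are to the combined protocol and SAP.

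- **Cases, testing.** Section 3.1: "All participants will undergo a clinical assessment, and immunologic and serologic testing for pneumococcus, tetanus, pertussis and varicella". Section 4.2, Visit 1, lists "antibody titres to the following vaccine antigens: tetanus toxoid, pertussis toxin (PT), varicella, and pneumococcal serotype-specific IgG" with no condition on earlier vaccination.
- **Controls, testing.** Section 4.2, Controls: "antibody titres to tetanus, PT, varicella, and pneumococcal serotypes, based on the vaccinations received".
- **Target population.** Objective 1 (section 2) asks about titres to pneumococcal serotypes, tetanus, pertussis toxin and "varicella in previously immunized children diagnosed with ALL", compared with immunocompetent age-matched controls.
- **Entry.** Apart from recent PPV23, the only case criterion on vaccines received is "No receipt of pneumococcal or tetanus-containing vaccines since completing chemotherapy" (3.2.1). For the other objectives cases are vaccinated whatever their history: "They will then be immunized with PCV13, DTaP-IPV-Hib, regardless of immunization history" (3.1). Control inclusion is "Children 3-18 years of age, age-matched to cases" plus language and consent (3.2.2), and matching is on age alone: "Controls will be frequency age-matched to cases to ensure that the age distribution of cases and controls is similar" (3.2.3).
- **Analysis.** Section 6.3.1 makes the baseline proportion at or above 0.35 µg/ml for the PCV13 serotypes tested, cases against controls, a primary outcome. Section 6.4 reports baseline results for both groups by interval since last vaccination. It names no immunized subset and no denominator.

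**The concern.** A case-control difference can be read in one of two ways. It can compare children who received the relevant vaccine, which is objective 1, or it can compare all children, which is the total difference. If controls are tested according to their own vaccines and cases are tested for everything, the comparison is neither. Unvaccinated cases count and unvaccinated controls are missing.

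The problem is sharpest at serotype level. Section 1.5 says that most children finishing chemotherapy would have had PCV7 in infancy and that many would never have had PCV13 or PPV23. Such a case is previously immunized against pneumococcus, yet has had no dose covering the serotypes outside PCV7. At stake is a primary outcome: a deficit in cases could partly reflect which vaccines were given rather than loss of antibody after chemotherapy.

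**Working it through.** **1. The passages side by side, for one serotype that is in PCV13 but not in PCV7.**

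| Child | Case | Control (plain reading of 4.2) |
|---|---|---|
| Had PCV13 | tested, counted | tested, counted |
| Had PCV7 only | tested, counted | not tested, missing |
| Had no pneumococcal vaccine | tested, counted | not tested, missing |

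Reading objective 1 into section 6.4 would remove the case in the last row but not the one in the middle row. Stratifying by interval since last vaccination does not settle it either. A never-vaccinated child has no interval, and 6.4 does not say that the interval is counted from a dose containing the serotype in question.

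**2. How many serotypes are exposed.** Section 5.2 lists 14 tested serotypes and says 3 are only in PPV23, so 14 − 3 = 11 remain. The same section gives the number in both vaccines as 10 but names 9, so the count is uncertain. Taking PCV7 as seven serotypes, those outside it number at least 11 − 7 = 4 (or 10 − 7 = 3, or 9 − 7 = 2, on the other counts).

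**3. The plan's own power figure.** Inputs from section 6.2: 75 cases, 75 controls, 60% of controls protected, 20-point difference, 77% power. A two-sided 5% level is assumed because none is stated.

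Power = Φ[(|p1 − p2| − 1.96·s0)/s1], with s0 = √(2p̄(1 − p̄)/n) and s1 = √((p1(1 − p1) + p2(1 − p2))/n).

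For 60% versus 80% and n = 75: s0 = √(2 × 0.21/75) = 0.0748, s1 = √(0.40/75) = 0.0730, and Φ[(0.20 − 0.1467)/0.0730] = Φ(0.730) = 76.7%. The stated 77% is reproduced in this direction. With cases at 40% the same formula gives 69.1%.

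**4. When the mismatch would matter (illustration, not an estimate).** Assumptions, none from the documents except the 60%: 60% of vaccinated children protected in both groups, a share u of cases without a vaccine containing the serotype, a proportion p of those cases protected (40% or 20%), and 75 tested per group.

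Case proportion = (1 − u) × 0.60 + u × p. For u = 0.20 and p = 0.20 this is 0.48 + 0.04 = 0.52, a gap of 8 points with no true difference among vaccinated children.

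| u | Gap in points (p = 40%, 20%) | Rejection rate of a 5% test |
|---|---|---|
| 2% | 0.4, 0.8 | 5.0%, 5.1% |
| 5% | 1.0, 2.0 | 5.2%, 5.7% |
| 20% | 4.0, 8.0 | 7.8%, 16.6% |

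The rate reaches 10% only when u is about 26% (p = 40%) or 13% (p = 20%). The standard error of the difference is about √(2 × 0.24/75) = 8 points.

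**5. What restriction costs.** The formula in step 3 with fewer children per group gives:

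| n per group | 60% vs 80% | 60% vs 40% |
|---|---|---|
| 75 | 76.7% | 69.1% |
| 60 | 67.0% | 59.3% |
| 38 | 47.6% | 41.3% |

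**The case against.** The best reply is that objective 1 limits cases to previously immunized children and section 4.2 limits controls by vaccines received, so together they already put the same kind of limit on both groups. Interval strata presuppose a prior dose and fit that intention. The phrase in 4.2 may also only explain the word baseline, which the text puts in quotation marks. Section 5.2 gives a single antigen panel, and section 8.1.2 budgets serology for cases and controls alike. On that reading testing is uniform.

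Part of this stands. The wording is ambiguous, and selective testing of controls cannot be asserted as fact. But the harmless reading still leaves 6.4 without objective 1's population. The joint reading still fails at serotype level, because a PCV7-only case remains in where a PCV7-only control would not.

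Two practical objections also stand. Restricting the main comparison is what corrects it, and wider control testing then serves mainly the sensitivity analysis. Restriction also removes most children exactly where the issue matters most. Since the product received depends on birth year, it may disturb the age match in those subsets as well.

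A reader might infer that any effect must count against cases. The documents give no titres for unvaccinated children, and for varicella past infection can make an unvaccinated child seropositive. A reader might also want a prior dose as an entry criterion, but cases are deliberately enrolled whatever their history for the other objectives, so the limit belongs in the analysis. Nor does the point call for controls and a case-status term in the planned predictor models. That is a separate modelling choice, and several predictors in section 6.3.2 (age at diagnosis, risk category, treatment protocol, time to remission) do not exist for controls.

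**Conclusion.** The concern holds as an undefined and, on the plain reading, unequal denominator in a primary baseline comparison. It does not show that the result will be biased by any given amount. If children without the relevant vaccine have lower pneumococcal titres, cases would tend to look less protected. The size cannot be computed, because the documents give no share of children vaccinated per serotype. Under the stated assumptions it is negligible at 2–5% of cases affected and becomes noticeable only at shares of roughly 13–26%. Section 1.5 makes larger shares plausible for serotypes outside PCV7 but gives no figure. Doses missed because of chemotherapy are partly a consequence of ALL, so some of such a gap would be a real total difference, not an error. It is worth correcting because one rule for both groups removes the ambiguity using records already obtained for both.

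**What to change.** **Section 6.4.** For objective 1, limit the baseline case-control comparison for each antigen or serotype, in both groups, to children with at least one documented dose of a vaccine containing it. State the resulting denominators. The interval strata, counted from such a dose, are then defined for every child in the main comparison.

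**Section 4.2, Controls.** Reword so that controls are tested for the same antigens and serotypes as cases. Report the comparison of all tested children as a sensitivity analysis.

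**Cost.** A few sentences and some extra control assays on serum already drawn. Controls whose blood is already being taken give 3–10 ml (section 7.1), against up to 5 ml for serology (section 4.3.2), so the smallest draws may need an assay order. Testing all controls costs no power; restricting the comparison does, as shown in step 5 of the working. The age distribution of each restricted set should be shown alongside its denominator. Eligibility, vaccines and visits are unchanged.
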